#### *Randomization*

The hearing screener, nurse, or volunteer will drop off tablets with participants, and only after the participants agree to participate by completing the tablet based consent will they be assigned to one of the four treatment conditions. The TMW-Newborn Web Platform will house the randomization tool that will randomize each participant into one of four treatment groups:

1. Long TMW-Newborn intervention video without questions interspersed,
2. Long TMW-Newborn intervention video with questions interspersed,
3. Short TMW-Newborn intervention video without questions interspersed, or
4. Short TMW-Newborn intervention video with questions interspersed.

There is equal likelihood of each randomization condition occurring.

#### **Participants**

Participants will include a goal of 10,000 new mothers at Sacred Heart Hospital, University of Chicago Medical Center, and Baptist Hospital-Pensacola. 2,500 will be randomized into each of the four implementation conditions outlined above.

#### **Exclusion criteria**

Individuals that do not have a live birth at Sacred Heart Hospital, University of Chicago Medical Center, or Baptist Hospital-Pensacola or do not receive the UNHS at one of these locations will not be eligible for this study.

#### **Payment**

Participants will not be compensated.

#### **Risks and Benefits**

Risks are minimal as testing only involves answering a questionnaire and providing demographic information. The data will be stored in password-protected computers and stored in locked file cabinets. Benefits include increased knowledge of the importance of early childhood language and cognitive development, and increased understanding of the Universal Newborn Hearing Screening and the importance of prompt follow-up after failed hearing screens.

#### **Analysis**

Paired t-tests will be used to analyze total survey scores before and after intervention. ANOVAs will be used to evaluate differences in outcomes based on SES and other variables in various experimental groups.

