### **Purpose**

The purpose of the proposed research is to perform testing of the Thirty Million Words Initiative Newborn Intervention (TMW-Newborn) with the primary goal of evaluating various implementation methods.

We hypothesize that the TMW-Newborn intervention will:

1. Significantly impact parent knowledge regarding the importance of UNHS follow-up
2. Significantly impact parent knowledge of child development

Additionally, we hypothesize that:

3. The 7-minute version of the video with questions interspersed will most significantly improve parent knowledge of child development
4. There will be no significant differences in effectiveness of the Spanish and English versions of the TMW-Newborn intervention

The hypotheses rely on the existing research data supporting the idea that parental understanding and beliefs will alter parental behavior, and consequently, that increased parental linguistic input will impact their child's cognitive development.

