### **Protocol**

We propose to perform a randomized implementation trial to evaluate the efficacy of various implementation methods of the TMW-Newborn educational intervention. The study will be

conducted in temporal proximity to the administration of the universal newborn hearing screen.

After routine delivery, postpartum mothers are admitted to the mother-baby unit for 48-72 hours. At Sacred Heart Hospital, study participation will be offered to every postpartum mother prior to discharge by a hearing screening technician, registered nurse, or registered hospital volunteer during the patient's hospital stay. Study participation will be offered to every mother whose child is receiving the hearing screening at the University of Chicago Medicine and Baptist Hospital-Pensacola. At the University of Chicago Medicine, study participation will be offered by a research assistant or hearing screening technician. At the Baptist Hospital-Pensacola, study participation will be offered by a nurse. The technician, nurse, or registered volunteer will give each mother an electronic tablet with the HIPAA Compliant TMW-Newborn Tech Platform that houses the TMW-Newborn intervention.

The patient experience through the TMW-Newborn intervention within the TMW Tech Platform is as follows:

- Participant selects language (English or Spanish) for viewing videos and completing surveys;
- Participant views Welcome and Consent Video, in which [name] (in English) or another health professional (in Spanish) introduce the study, explain participation, outline risks;
- Participants who agree to participate will then be randomized into one of four conditions:
  - Long TMW-Newborn intervention video without questions interspersed,
  - Long TMW-Newborn intervention video with questions interspersed,
  - Short TMW-Newborn intervention video without questions interspersed, or
  - Short TMW-Newborn intervention video with questions interspersed.
- Participant completes pre-intervention surveys: Baby SPEAK and non-identifying demographics items. These surveys take approximately 10 minutes to complete.
- Participant views TMW-Newborn intervention video, according to her randomized assignment outlined above.
- Participant completes post-intervention surveys: Baby SPEAK, UNHS, and fidelity of implementation.

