The hearing screener, nurse, or volunteer will be notified via the TMW Tech Platform to pick up the tablet from the participant upon intervention completion or whenever the participant opts out.

No identifying information is collected within the TMW-Newborn web platform, and the hearing screening technicians will not be able to see or access any of the participants' responses.

This study protocol will only be used at Sacred Heart Hospital, University of Chicago Medical Center, and Baptist Hospital-Pensacola.

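### The primary question is which video format works best, but the Analysis section states no format factor, outcome, baseline adjustment or hypothesis 3 contrast

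*Combined protocol and SAP*

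**What the plan says.** The Purpose section describes testing the intervention "with the primary goal of evaluating various implementation methods", and the Protocol section proposes a "randomized implementation trial to evaluate the efficacy of various implementation methods of the TMW-Newborn educational intervention". The Randomization section allocates mothers with equal probability to four formats: long or short video, each with or without embedded questions. The Participants section sets a goal of 10,000 mothers, 2,500 per format.

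Hypothesis 3 is a between-format claim: "The 7-minute version of the video with questions interspersed will most significantly improve parent knowledge of child development". Hypothesis 2 is a separate claim that the intervention affects parents' knowledge of child development.

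Baby SPEAK is collected twice: "Participant completes pre-intervention surveys: Baby SPEAK and non-identifying demographics items" and, after the video, "Participant completes post-intervention surveys: Baby SPEAK, UNHS, and fidelity of implementation".

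The whole Analysis section is two sentences: "Paired t-tests will be used to analyze total survey scores before and after intervention", and "ANOVAs will be used to evaluate differences in outcomes based on SES and other variables in various experimental groups". No other part of the document gives an alpha level, a primary comparison, a contrast or a multiplicity rule.

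**The concern.** A paired t-test, pooled or run within each arm, asks whether scores moved. It has no group term, so it is silent on which format moved them more. All four arms can show a highly significant gain while the formats are identical.

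The ANOVA sentence is the only one that could carry the between-format comparison. SES is the only variable it names, and the experimental groups appear as the setting rather than as a stated factor. It can be read as SES effects within each arm, or as including format. On either reading it leaves open whether the outcome is post score or change, whether baseline enters the model, and how the hypothesis 3 arm is to be compared with the other three. An omnibus F test across four arms has no direction, so it cannot by itself support a claim that one named arm is best.

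At stake is the trial's main question. With outcome and contrast open, both could be settled after the data are seen. Precision available from a baseline measure already collected could also go unused.

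**Working it through.** **Inputs from the documents.** Four arms, equal allocation, 2,500 per arm; 4 x 2,500 = 10,000, which agrees with the stated goal. No power calculation is given, so there is none to reproduce.

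**Assumptions.** Two-sided alpha 0.05; effects d in SDs of one Baby SPEAK score; equal pre and post SDs; pre-post correlation r = 0.6; all 2,500 per arm complete both surveys.

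**Step 1: what the paired test can show.** Suppose every arm has the same true gain of 0.1 SD of the change score. Each paired test then has expected z = 0.1 x sqrt(2500) = 5, and power Φ(5 − 1.96) = 0.9988. All four are significant with probability 0.9988^4 = 0.995. Simulation (1,000 runs for each of the gains 0.1, 0.2 and 0.5) gave all four significant in 99.5% to 100% of runs. An ANOVA on change by arm rejected in 4.8% to 5.4%, its nominal rate. Significant before-after tests therefore carry no information about format.

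**Step 2: what an omnibus F can show.** Take one arm differing from the other three by d. The noncentrality is 2,500 x 0.75 x d², with 3 and 9,996 df. Power on post scores is 42%, 84% and 97% at d = 0.05, 0.08 and 0.10. It is the same whether that arm is better or worse, because d enters squared.

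**Step 3: one pairwise contrast.** Power = Φ(d x sqrt(n/2)/s − 1.96), where s is the SD of the analysed quantity:
- post score: s = 1
- change score: s = sqrt(2(1 − r)) = 0.894
- ANCOVA: s = sqrt(1 − r²) = 0.8

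For example, at d = 0.08, d x sqrt(1250) = 2.828. Dividing by s gives 2.828, 3.162 and 3.536, so power is Φ(0.87) = 81%, Φ(1.20) = 89% and Φ(1.58) = 94%.

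| d (SD) | Post score | Change score | ANCOVA |
|---|---|---|---|
| 0.05 | 42% | 51% | 60% |
| 0.08 | 81% | 89% | 94% |
| 0.10 | 94% | 98% | 99% |

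At d = 0.08, varying r from 0.5 to 0.7 moves change-score power from 81% to 95% and ANCOVA power from 90% to 98%.

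**Step 4: a rule requiring the named arm to beat all three others.** With each contrast at one-sided 0.025, power is the integral over a of φ(a) x the product over the three rivals of Φ(a + d_j x sqrt(n)/s − 1.96 x sqrt(2)), where d_j is the named arm's advantage over rival j. ANCOVA results at r = 0.6:

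| d (SD) | Only the named arm differs (0, 0, 0, d) | Additive pattern (0, d/2, d/2, d) |
|---|---|---|
| 0.08 | 87% | 26% |
| 0.10 | 98% | 44% |
| 0.15 | over 99% | 85% |

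In the additive pattern d is best versus worst arm, and the nearest rivals are only d/2 behind. On post scores the additive figures are 15%, 26% and 63%. The rule's false-claim rate is about 0.2% if all arms are equal and at most 2.5% if the named arm ties with another.

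**The case against.** The strongest reply is that the only experimental groups in the document are the four formats, so an ANOVA of outcomes in those groups naturally includes a comparison of formats, and a competent analyst would add follow-up contrasts. The first half of this stands. A reader might infer that no between-format comparison is planned, or that only paired tests will be run. The text does not support that, because it commits to ANOVAs as well. What remains is that the factor, outcome, adjustment and contrast are unstated for the primary question.

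A reader might also infer that the named arm will be declared best whenever F is significant and its mean is highest, and object that this would often be wrong when two arms tie. The document states no such rule, and that error needs an exact tie, so it should not be charged to the plan.

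The paired t-tests are not misplaced altogether: they match the before-after question in hypothesis 2. Their limit is that every arm receives a TMW video, so change cannot be separated from repeat testing within this trial. The absence of a significant increase in the control group, reported under Previous Research, is only indirect support.

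It is also fair that ANCOVA over a change score is a gain in precision, not a correction of an error, and that the gain is small for larger differences. Finally, tablets are collected "upon intervention completion or whenever the participant opts out". Opt-out could differ by video length, and the power figures above do not allow for that.

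**Conclusion.** The point holds as under-specification of the primary between-format analysis. The paired tests do not compare arms. The ANOVA sentence may include format but states no factor, outcome, baseline adjustment or hypothesis 3 contrast, and an omnibus F alone does not establish a best arm.

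It would go too far to conclude that the trial cannot answer its question. Randomization, sample size and the paired Baby SPEAK measurements are all adequate to support a direct comparison.

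Under the stated assumptions, baseline adjustment raises pairwise power from 42% to 60% at 0.05 SD and from 81% to 94% at 0.08 SD. At 0.10 SD it adds only about five points (94% to 99%). Whether differences this small matter is not addressed in the documents. The power of an all-three rule depends heavily on the pattern of means (87% versus 26% at 0.08 SD), so the choice of decision rule is a real trade-off and should be made in advance.

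**What to change.** Add to the Analysis section:

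1. The primary between-format analysis is an ANCOVA of post-video Baby SPEAK on length, questions and length x questions, adjusted for pre-video Baby SPEAK.
2. Hypothesis 3 is tested by pre-specified contrasts of the named arm with each of the other three, reported with 95% confidence intervals.
3. One decision rule is stated. Requiring all three contrasts to be significant is one option: it needs no alpha split, but it is conservative. A multiplicity-adjusted set of contrasts is another.
4. The paired t-tests are kept for the before-after question in hypothesis 2, with a note that no arm goes without a TMW video.
5. The mothers to be analysed are defined, including how those who opt out before the second survey are handled.

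In hypothesis 3, state which randomized arm is the seven-minute version. The Randomization section labels the videos only as long or short, so the named arm cannot be identified from the text.

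The cost is a few sentences and one label. No new data or participants are needed, because Baby SPEAK is already collected before and after the video.

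### As written, the four video formats would by default be compared only among mothers who reached the post-survey, and no planned analysis compares completion by format.

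*Combined protocol and SAP*

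**What the plan says.** The Purpose section describes the study as testing the intervention "with the primary goal of evaluating various implementation methods". Hypothesis 3 ranks the formats: "The 7-minute version of the video with questions interspersed will most significantly improve parent knowledge of child development".

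The Protocol and Randomization sections set the order of events. A mother consents on the tablet and is randomised to a long or short video, with or without questions. Before the video, "Participant completes pre-intervention surveys: Baby SPEAK and non-identifying demographics items". She then watches the assigned video, and afterwards "Participant completes post-intervention surveys: Baby SPEAK, UNHS, and fidelity of implementation". Staff are told to "pick up the tablet from the participant upon intervention completion or whenever the participant opts out". No later contact is described, and no identifying data are collected. The Participants section states that "2,500 will be randomized into each of the four implementation conditions outlined above".

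The Analysis section has two sentences. The first is "Paired t-tests will be used to analyze total survey scores before and after intervention". The second is "ANOVAs will be used to evaluate differences in outcomes based on SES and other variables in various experimental groups". Neither names the four-format comparison. I infer it from the reference to experimental groups together with hypothesis 3.

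**The concern.** A paired t-test looks at change within mothers and cannot rank formats, so the ranking rests on the ANOVAs. Run on the observed post or gain scores, an ANOVA drops every mother without a post score. The arms differ in length and in interruptions, and these could affect who stays to the end.

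Two things are at stake. First, if leavers would have gained less than finishers, a format that loses more of them looks better than it is; if leavers would have gained more, it looks worse. The randomised comparison becomes a comparison of self-selected finishers. Second, completion is itself a result in a trial of implementation methods. A format could come first on knowledge among finishers while fewer mothers finish it, and no planned output would show this. The fidelity items cannot fill the gap, because they too are collected after the video.

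**Working it through.** **The plan's own figure.** 4 × 2,500 = 10,000, which agrees with the recruitment goal. No alpha, power, SD, effect size or drop-out rate is given, so the sample size cannot be rebuilt from a power formula.

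**Inputs.** n = 2,500 per arm is from the Participants section. Everything else is assumed: two-sided alpha 0.05, two equally effective formats A and B, one unadjusted pairwise test, and the drop-out rates and gaps below. The unit is the between-mother SD of the gain score.

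- a, b = share of randomised mothers in A and B without a post score.
- g = mean gain of finishers minus mean gain that leavers would have had.

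**Formulas.** The finisher mean equals the all-mother mean plus g × drop-out, so bias (B minus A) = gB·b − gA·a. SE = √[1/(2500(1−a)) + 1/(2500(1−b))]. Type I error = Φ(−1.96 − bias/SE) + 1 − Φ(1.96 − bias/SE).

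| Drop-out A v B | gA, gB | Bias (SD) | SE | Type I error |
|---|---|---|---|---|
| 10% v 10% | 0.3, 0.3 | 0 | 0.0298 | 5.0% |
| 10% v 12% | 0.3, 0.3 | 0.006 | 0.0300 | 5.5% |
| 5% v 10% | 0.3, 0.3 | 0.015 | 0.0294 | 8.0% |
| 10% v 20% | 0.3, 0.3 | 0.030 | 0.0307 | 16% |
| 10% v 20% | 0.5, 0.5 | 0.050 | 0.0307 | 37% |
| 15% v 15% | 0.2, 0.4 | 0.030 | 0.0307 | 16% |
| 10% v 20% | −0.3, −0.3 | −0.030 | 0.0307 | 16% |
| 10% v 20% | 0.4, 0.2 | 0 | 0.0307 | 5.0% |

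The sixth row shows that equal completion does not remove the risk. The seventh shows that the sign can reverse, and the last that the two products can cancel. If drop-out is unrelated to gain in both arms, the bias is zero at any rate.

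**Scale.** The difference detectable with 80% power and full data is 2.802 × √(2/2500) = 0.079 SD. Every bias above is smaller, so the danger is a false ranking of similar formats and not a hidden large effect.

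**What baseline adjustment can do** (approximate, ignoring any gain in precision). If baseline explains half of the gap, the 10% v 20% cases keep a bias of 0.015 to 0.025 SD and a type I error of 8% to 13%. If it explains all of the gap, the bias is 0 and the error 5%.

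**Is a completion comparison informative?** The SE of the difference is √[a(1−a)/2500 + b(1−b)/2500]. At 10% v 12% this is 0.00885, a 95% half-width of 1.7 percentage points. At 10% v 20% it is 0.0100, a half-width of 2.0 points. A contrast of 10% v 12.5% has about 80% power.

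**Why a tipping point and not a fixed range.** Let δ = leaver minus finisher gain. The shift in the estimated difference is δB·b − δA·a. With δ free between −0.5 and +0.5 in each arm, the largest shift is 0.5(a+b), which is 0.05 at 5% in both arms and 0.10 at 10% in both. A conclusion changes when the shifted difference crosses the significance threshold, 1.96 × SE, about 0.057 to 0.060 SD at these drop-out rates. So even at 5% in both arms, a significant difference of up to about 0.05 + 0.057 = 0.107 SD could be overturned. Reporting the tipping value avoids choosing a range. For example, take an observed difference of 0.079 SD in favour of B at 10% v 20% and the same δ in both arms. Significance is lost when 0.079 + δ(0.20 − 0.10) = 0.060, that is at δ = −0.19 (SE held fixed).

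**The case against.** **The tests need not be limited to finishers.** A reader might infer that the planned methods can use only mothers with a post score. The Analysis section is silent on missing scores, and baseline Baby SPEAK and demographics could support imputation. This stands: the text supports only that finishers are what the tests would use by default.

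**Loss may be trivial.** This is one session, and the only video length stated is 7 minutes. The one exit described in detail is refusal at consent, before randomisation. This stands in part. Nothing in the documents supports 10% v 20%, and a reader who takes 37% as an estimate goes beyond them. But the Protocol does provide for opting out at any time, and nothing says that loss will be low.

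**Multiplicity control would shrink the figures.** With Bonferroni over six pairs, the two 16% cases with positive gaps fall to about 5% and the 37% case to about 16%. No such control is planned, however, and the nominal rate per pair would then be 0.05/6 = 0.8%, so the relative inflation remains.

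**Low drop-out would settle it.** A reader might set the largest shift under ±0.5 SD against the detectable difference and conclude that below about 8% drop-out in both arms (0.5 × 0.16 = 0.08 SD) nothing could change. That is the wrong yardstick, because conclusions turn on the significance threshold and not on the detectable difference.

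**Restricting to baseline submitters is not neutral.** Mothers are randomised before the roughly 10-minute pre-survey, and the documents do not say whether the format is visible by then. A reader might assume that this restriction precedes any exposure to format; the text does not establish it. This objection stands and determines the denominator in the fix.

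**Conclusion.** The concern holds as a gap in the plan. Mothers can leave after randomisation, the only post score follows a video that differs by arm, and the stated tests would by default compare finishers with no look at completion by format. A demonstrated bias would be a stronger claim, and the documents do not support it: they give no drop-out rate and no evidence that loss differs by format or relates to gain.

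Under the assumed rates, for one unadjusted pairwise test of equally effective formats with 2,500 mothers per arm, the bias is 0 to 0.05 SD in size and type I error runs from nominal to 37%. The mild case (10% v 12%, gap 0.3 SD) is almost nominal at 5.5%. The large planned sample does not remove such a bias; it makes a small one more likely to reach significance. The plan should be changed, because the comparison at risk is the main purpose of the trial and the remedy is cheap.

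**What to change.** Add one paragraph to the Analysis section.

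1. Compare the four assigned formats with an ANCOVA of post Baby SPEAK on arm, adjusted for baseline Baby SPEAK. State that it is fitted to mothers with both scores and corrects only for drop-out that baseline predicts.
2. From platform records, report by arm the numbers randomised, submitting baseline, finishing the video and submitting the post-survey. Compare completion across arms with 95% intervals, and show it beside the knowledge result. Use all randomised mothers as the main denominator, so that losses before baseline are visible, and baseline submitters as a secondary one.
3. As a supporting analysis, vary the non-completers' assumed gain in both directions and separately by arm, and report the values at which the conclusion changes. Do this even if completion is equal across arms.

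The time of randomisation need not change, and no visits or survey items are added. The cost is a little more analysis. The platform signals completion and opting out; that it can store these events by arm is an assumption to confirm. The knowledge result will have to be read together with completion, and if drop-out is high the ranking of formats may be left undecided.

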But the tragedy for these children is not unalterable. It is neither genetics nor a lack of potential that lies at the heart of this inequity; it is parental knowledge. In 2008, Rowe demonstrated that the relationship between socioeconomic status and parental communication ability is mediated by parental knowledge (Rowe 2008). Other studies have corroborated this, showing that the effect of socioeconomic status on a child's vocabulary was primarily dictated by maternal speech (Hoff 2003). Encouragingly, studies have also demonstrated that a well-planned, parent-directed language intervention in low-income populations may have a positive effect with parents increasing their use of facilitative language with their children (Oneil-Pirozzi, 2009).

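### The planned ANOVAs state neither a baseline covariate nor a modifier-by-arm interaction, so they need not show who benefits from which video version

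*Combined protocol and SAP*

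**What the plan says.** The Analysis section of the combined protocol and SAP has two sentences. The first is "Paired t-tests will be used to analyze total survey scores before and after intervention". It uses the baseline score but contrasts no arms. The second is "ANOVAs will be used to evaluate differences in outcomes based on SES and other variables in various experimental groups". Any comparison between video versions, or between subgroups, has to rest on that second sentence.

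The Protocol section shows what data exist. Before the video, "Participant completes pre-intervention surveys: Baby SPEAK and non-identifying demographics items". Afterwards, "Participant completes post-intervention surveys: Baby SPEAK, UNHS, and fidelity of implementation". Baby SPEAK therefore has a baseline, while UNHS is listed only after the video. The Randomization section sets equal allocation: "There is equal likelihood of each randomization condition occurring".

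In the Purpose section, hypothesis 3 names one version as the most effective, which is a comparison between arms. Hypothesis 4 expects the Spanish and English versions to be equally effective. Language is the only modifier that the hypotheses name; none concerns SES.

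**The concern.** An ANOVA of outcome by SES asks whether SES groups differ. It does not ask whether the effect of video length or of interspersed questions differs by SES. Only a modifier-by-arm interaction answers that, and the plan states none.

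The background gives a reason to expect a gap in knowledge before the video, since it reports that "the relationship between socioeconomic status and parental communication ability is mediated by parental knowledge". If post-video scores are compared by SES, that gap carries through even when every mother gains the same amount.

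The trial exists to choose among implementation methods, and its background claims potential relevance to SES disparities. A difference in score level by SES could be taken as a difference in benefit. The plan also leaves open whether the baseline score, which is already collected, enters this analysis, and it sets no limit on which further variables are examined.

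**Working it through.** **Inputs from the plan.** The Participants section states "Participants will include a goal of 10,000 new mothers at Sacred Heart Hospital" (among three hospitals) and "2,500 will be randomized into each of the four implementation conditions outlined above". The arithmetic agrees: 4 × 2,500 = 10,000. There is no power calculation to reproduce.

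**Assumptions, because the plan gives no figures.** Two-sided alpha 0.05, power 80%, SD 1, two equal SES groups (1,250 v 1,250 in an arm), baseline SES gap d of 0.1 to 0.3 SD, pre-post correlation r of 0.5 or 0.7 (0.3 added in step 5), no missing data. Every mother gains the same amount, so no version suits any group better.

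**1. Post-video score within one arm.** The standard error of the SES difference is √(1/1,250 + 1/1,250) = 0.04 SD. The chance of a significant result is Φ(d/0.04 − 1.96).
- d = 0.1: Φ(2.5 − 1.96) = Φ(0.54) = 0.705.
- d = 0.2: Φ(5.0 − 1.96) = Φ(3.04) = 0.999.

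A simulation of four arms of 2,500, with 1,000 trials per setting, gave 69% to 72% and 99.8% to 99.9%.

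**2. Change score within one arm.** With equal gains the expected SES difference is zero. The simulated rate of significance was 3.6% to 6.6%, so the baseline gap does not drive the result.

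**3. Baseline adjustment within one arm, without an interaction.** The expected adjusted SES difference is d(1 − r), with standard error 0.04 × √(1 − r²). For d = 0.1 and r = 0.5 this is 0.05/(0.04 × 0.866) = 1.44, and Φ(1.44 − 1.96) is about 0.30. The simulation gave 20% to 30% at d = 0.1 and 56% to 82% at d = 0.2. Adding the baseline score alone is therefore no cure.

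**4. One pooled model with baseline and an SES-by-arm interaction (3 df).** The simulated false-positive rate was 4.0% to 5.7% across all settings. The interaction is the essential part.

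**5. Precision.** Residual variance is 1 for the post score, 2(1 − r) for the change score and 1 − r² with baseline adjustment.
- Against post scores, adjustment cuts variance by r²: 25% at r = 0.5 and 49% at r = 0.7.
- Against change scores, it cuts variance by (1 − r)/2: 25% at r = 0.5 and 15% at r = 0.7.

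For a balanced SES-by-length (or SES-by-questions) interaction there are 10,000/4 = 2,500 mothers per cell. The standard error is √(4/2,500) = 0.04, and the detectable interaction is (1.96 + 0.84) × 0.04 = 0.112 SD unadjusted. Multiplying by √(1 − r²) gives 0.107, 0.097 and 0.080 SD at r = 0.3, 0.5 and 0.7. On change scores the multiplier is √(2(1 − r)), which gives 0.112 SD at r = 0.5 and 0.087 SD at r = 0.7. For comparison, the unadjusted main effect of length (5,000 v 5,000) has standard error √(2/5,000) = 0.02 and a detectable difference of 2.80 × 0.02 = 0.056 SD.

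**The case against.** A reader might infer that the plan will run separate ANOVAs inside each arm, that it omits the baseline score by design, or that it will judge differential benefit by which arms reach significance. The documents support none of these. The wording about experimental groups also fits a single ANOVA across arms with an interaction, so the accurate statement is that an interaction is not specified. The outcome form is not stated either. Change is at least as natural a reading, because the preceding sentence concerns scores before and after the video and hypothesis 3 concerns improvement. Nothing in the Analysis section says how arms would be compared on significance, or that an SES difference would be read as differential benefit.

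It is also fair to say that a difference in post-video level by SES is a true answer to the question of whether outcomes differ by SES. At 10,000 mothers, the precision gained by baseline adjustment is a refinement.

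Two things remain. The sentence admits both a valid and a misleading analysis and does not choose between them. And under either outcome, an SES comparison within arms does not test whether length or questions work differently by subgroup.

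**Conclusion.** The point holds as one of unspecified method and should be settled before the data are analysed. The prior-knowledge artefact is conditional on within-arm tests of post-video scores. There, a baseline gap as small as 0.1 SD would usually give a significant SES result with no difference in benefit. On change scores the artefact is absent, and what is lost is precision (15% to 25% of residual variance at r = 0.7 to 0.5) and a test of the right question. The SD scale, SES split, baseline gaps, correlations and alpha are all assumptions. The documents do not show that a wrong analysis is intended, only that none has been chosen.

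**What to change.** For Baby SPEAK, replace the ANOVA sentence with one model on all randomised mothers with data: post-video score on pre-video score, length, questions, length × questions, language, SES (one stated measure from the demographics items) and site.

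- Use the length and questions terms and their interaction for the between-version comparison in hypothesis 3.
- Judge any difference in version effect by subgroup only by modifier × length and modifier × questions interactions, added to the model and reported with 95% CIs. Pre-name language (because of hypothesis 4) and SES as the modifiers. Report further variables as exploratory.
- For hypothesis 4, also report the language difference in gain with an estimate and CI from the same model. That term compares gains at equal pre-video score, and step 3 shows that it can differ from zero when mean gains are equal, so give the mean gains by language beside it. Mothers choose their language, so this comparison is not randomised.
- Describe language and SES differences in score level as observational.
- For UNHS, which has no pre-video measure, compare arms with the same factorial model without a baseline score.

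This changes analysis wording only and uses data already planned. The cost is power: interactions need about 0.11 SD unadjusted, or 0.08 SD at an assumed correlation of 0.7, against about 0.056 SD for an unadjusted main effect. Fewer subgroup findings could be claimed.
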